#### 10.7.4 Data collected during Visit 1 – MR exam

- Eligibility
- Signed Informed Consent / Assent
- Demographics
  - o Age
  - o Sex
- MRI Examination
  - o Use of anesthesia
  - Use of contrast agents during investigational sequences
  - MRI performed according to CIP
  - Upload of MRI files
- Site-determined diagnosis
  - o Primary Pathology Group
  - o Summary of radiological findings
- Adverse Events
- Device Deficiencies

#### 10.7.5 Performance Variables and Measurements

#### 10.7.5.1 Radiological findings

The radiologist will be asked to interpret the case based on T1w, T2w, and T2w FLAIR images and choose the primary radiological finding class that they think is the reason behind the radiological findings in the images. There may be more than one pathology (or pathology options) in each case so the reader is asked to choose the most appropriate or significant pathology group. Not all patients are expected to have clinical findings, so a normal/no finding category is also included.

#### RADIOLOGICAL FINDING CLASSES

Infectious/Inflammatory/Demyelinating	
Vascular Disorders of the Brain	
Neuro Degenerative Disorders and Hydrocephalus	
Intracranial Neoplasms	
Traumatic Lesions	

Congenital Malformations

	Clinical Investigation Code:	Date
SyntheticMR	CIP-003, Version K	2023-12-21

Toxic and Metabolic conditions

Normal / No findings

The ground truth will be the site-determined diagnosis on the basis of the results of conventional MR images and standard of care by neuroradiologist. This means that the ground truth may be based on more information than what will be available for the readers in this clinical investigation, e.g. for the site determined diagnosis the neuroradiologist may also have access to DWI or SWI which will not be available in this clinical investigation.

#### 10.7.5.2 Image Quality

The radiologist will be asked to rate the image quality for the T1w and T2w images. A 5-point Likert scale will be used. Ratings of  $\geq 3$  will be considered clinically useable.

#### RATE IMAGE QUALITY

- 5 Excellent
- 4 Good
- 3 Acceptable
- 2 Poor
- 1 Unacceptable

#### 10.7.5.3 Legibility of anatomical structures

The radiologist will be asked to evaluate the legibility of anatomical structures in the T1w and T2w images. The anatomical structures are defined in the list below. Each anatomical structure will be rated on a binary scale (legible/illegible). Legibility is defined as the ability to see structures and margins associated with the key anatomic/morphologic feature to the extent necessary to be clinically usable.

#### ANATOMICAL STRUCTURES

Central sulcus

Cerebral peduncle

Corticomedullary junction

Head of caudate nucleus

Middle cerebellar peduncle

Posterior limb of internal capsule

# 10.7.5.4 Artifacts

The radiologist will be asked to record presence and type of artifacts per contrast weighting. Type of artifact can be chosen from the pre-defined list below. If the artifact is not defined in the list the reader is asked to describe the artifact.

#### **ARTIFACTS**

Motion		
In-folding and wrap-around		
Flow or phase-encoding		
Magic angle effect		
Water-fat shift / chemical shift		
Magnetic susceptibility artifact		
Low resolution		

Devicia AB Confidential

Low Signal to Noise

	Clinical Investigation Code:	Date
SyntheticMR	CIP-003, Version K	2023-12-21

Low tissue contrast

Other, please specify

# 10.7.6 Safety Variables and Measurements

The safety measurement will be the onset, severity, duration and frequency of AEs (anticipated and unanticipated), including determination of causality. Only events, which are new after the consent has been signed or have increased in severity after the consent has been signed, will be recorded. All AEs will be recorded and reported, and all data required both to assess the safety and to comply with the IRB and FDA requirements will be collected. All events will be followed up until resolved or judged as clinically stable according to the investigator or designee, if possible.

#### 10.7.7 Activities Performed by Sponsor

The Sponsor will provide instructions to site personnel on how to perform the investigational pulse sequences. This will take place during site initiation and thereafter as required, e.g. if new site personnel or any re-training is required.

### 10.7.8 Potential Confounding Factors

No potential confounding factors have been identified.

# 10.7.9 Future use of data obtained from subject

The anonymized MR images collected from the subjects may be used for future research, product development, and inventions by the Sponsor, hospitals, universities and other businesses.

	Clinical Investigation Code:	Date
SyntheticMR	CIP-003, Version K	2023-12-21

#### 11 MONITORING PLAN

A detailed description of monitoring activities will be provided in a separate, investigation-specific risk-based monitoring plan.

# 11.1 Subject Records and Source Data

Subject data recorded directly in electronic case report form (eCRF) (and not into the medical record) will be considered source data. It is the responsibility of the PI to record essential information in the medical records, in accordance with regional and national regulations and requirements. The origin of source data in this clinical investigation will be further specified in a separate document ("Source Data Location Agreement").

In general the following information should be recorded in the medical records:

- Investigation code, and or investigational title
- Subject ID
- That informed consent for participating in the clinical investigation was obtained, and the date of collection
- Diagnosis
- Visit number and visit date
- All AEs
- Treatments and medications
- Subject health service identification number, if applicable

The PI is responsible for ensuring the accuracy, completeness, legibility and timeliness of the data recorded in the eCRFs. Signed sections of eCRFs will be monitored on a regular basis.

# 11.2 Access to Source Data and Documentation

The PI should guarantee access to source documents for the monitor and auditors as well as for inspection by appropriate Regulatory Agencies, and Institutional Review Boards (IRBs), if required.

	Clinical Investigation Code:	Date
SyntheticMR	CIP-003, Version K	2023-12-21

#### 12 STATISTICAL CONSIDERATIONS

# 12.1 Statistical Design, Method and Analytical Procedures

#### 12.1.1 Analysis populations

- The full analysis set consists of all subjects with at least one pair of synthetic-conventional MR image readings from at least one reader.
- The pathological subgroup consists of all subjects with a pathological finding according to site-determined diagnosis.
- The control group consists of all non-pathological subjects, including both healthy volunteers and subjects classified as normal/no-finding according to site-determined diagnosis.
- The adult sub-population consists of all subjects aged 18–99 years.
- The pediatric sub-population consists of all subjects aged 0–17 years.

#### 12.1.2 General Statistical Methodology

Descriptive statistics of subject demographics, characteristics of readers, and performance endpoints will be summarized descriptively at the patient, reader and image level. Continuous variables will be described with mean, standard deviation, median, minimum, and maximum value, and categorical variables with numbers and percentages.

Statistical analyses will be performed on the patient level. Comparisons between conventional and synthetic MR images will be conducted using non-inferiority testing procedures.

The mean difference will be presented with corresponding two-sided 95% confidence interval. Non-inferiority will be established if the lower limit of the two-sided 95% confidence interval for the mean difference (i.e., intercept) is strictly greater than a pre-specified non-inferiority margin. The primary analyses will be performed on the full analysis set. Separate analyses on adult and pediatric sub-populations, and separate analyses by reader, will also be performed.

For the primary and secondary endpoints, a non-inferiority margin of -0.05 will be used. All tests will be one-sided and conducted at significance level  $\alpha$ =0.025. In case of a successful non-inferiority test for the two primary performance endpoints, the entire probability mass  $\alpha$ =0.025 will be transferred to the secondary performance endpoints in the order specified in Section 10.2.2 *Secondary performance endpoints*. Non-inferiority will then be declared for all secondary performance endpoints with a successful non-inferiority test until the first encounter of a non-successful non-inferiority test. Estimates and confidence intervals of remaining performance endpoints will be presented descriptively but not considered as confirmatory findings.

#### 12.1.3 Primary Performance Analysis

Sensitivity of pathological findings

The sensitivity of pathological findings will be calculated as the sample proportion of true positive (pathological) findings across all patients and readers. The difference in sensitivity between synthetic

	Clinical Investigation Code:	Date
SyntheticMR	CIP-003, Version K	2023-12-21

and conventional MR will be evaluated using non-inferiority testing procedures with GEE for binary variables as described in Section 12.1.1 General Statistical Methodology. A non-inferiority margin of -0.05 will be used.

# Specificity of pathological findings

The specificity will be calculated as the sample proportion of true negative (non-pathological) findings across all patients and readers. The difference in specificity between synthetic and conventional MR will be evaluated using non-inferiority testing procedures with GEE for binary variables as described in Section 12.1.1 General Statistical Methodology. A non-inferiority margin of -0.05 will be used.

Both primary endpoints will be tested at significance level  $\alpha$ =0.025, one-sided test. Non-inferiority of diagnostic accuracy with synthetic MR images compared to conventional MR images will be declared if non-inferiority is demonstrated in both primary endpoints.

#### 12.1.4 Secondary Performance Analyses

#### Diagnostic accuracy of radiological findings

The accuracy of radiological findings will be calculated as the sample proportion of correctly identified radiological findings (radiological finding class) across all patients and readers. The difference in accuracy between synthetic and conventional MR will be evaluated using non-inferiority testing procedures

A non-inferiority margin of -0.05 will be used, significance level  $\alpha$ =0.025, one-sided test. The radiological finding classes will be cross-tabulated for synthetic and conventional images vs site-determined diagnosis (ground truth).

#### Other secondary endpoints

The remaining secondary performance endpoints will be evaluated according to the methodology above in the following order:

- Sensitivity of pathological findings in adult sub-population
- Specificity of pathological findings in adult sub-population
- Diagnostic accuracy of radiological findings in adult sub-population
- Sensitivity of pathological findings in pediatric sub-population
- Specificity of pathological findings in pediatric sub-population
- Diagnostic accuracy of radiological findings in pediatric sub-population

In case of a successful non-inferiority test for the two primary performance endpoints, the entire probability mass  $\alpha$ =0.025 will be transferred to the secondary performance endpoints in the order listed above. Non-inferiority will be declared for all primary and secondary performance endpoints with a successful non-inferiority test until the first encounter of a non-successful non-inferiority test. Estimates and confidence intervals of remaining performance endpoints will be presented descriptively but not considered as confirmatory findings.

#### 12.1.5 Exploratory Analyses

# Legibility

The percentage of legibility for each of the anatomic structures will be cross-tabulated for synthetic vs conventional for the contrast weighted images (T1w, T2w).

# Artifacts

Each of the artifacts will be cross-tabulated synthetic vs conventional per contrast weighting (T1w, T2w). Any novel or previously unforeseen artifacts will be listed and described.

	Clinical Investigation Code:	Date
SyntheticMR	CIP-003, Version K	2023-12-21

Inter-rater and inter-method agreement of radiological findings

Each of the radiological finding classes will be cross-tabulated for synthetic vs conventional images, followed by calculation of percent agreement, Cohen's kappa coefficient, and Gwet's AC1 coefficient between methods and readers. Inter-method agreement will be analyzed to evaluate agreement between synthetic and conventional images, i.e., if the readers draw the same general conclusions regardless of image type. Inter-rater agreement will be calculated to evaluate how well the different readers agree with each other on the radiological findings when either synthetic or conventional images are used.

Image quality of T1w and T2w images

The difference in image quality score will be analyzed using linear mixed effects models as described in Section 12.1.1 General Statistical Methodology.

#### 12.1.6 Safety Analysis

Safety variables will be summarized descriptively.

# 12.1.7 Justification of choice of non-inferiority margin

A non-inferiority margin of -0.05 for the mean difference in sensitivity, specificity and diagnostic accuracy will be used.

# 12.2 Sample size

A total of 180 evaluable subjects (90 pathological, 90 controls) and 5 readers will be included in the study to obtain 80% simultaneous power in both primary endpoints using one-sided test, significance level  $\alpha$ =0.025, non-inferiority margin -0.05. The calculations are based on the following assumptions:

#### 12.3 Drop-out Rates

No drop-out is expected from the evaluable subjects.

For the healthy controls, a 10% drop-out is estimated considering incidental findings which will exclude subjects after scan, and some subjects not showing up the scheduled appointment.

# 12.4 Level of Significance and Power

All tests will be one-sided and conducted at significance level  $\alpha$ =0.025. The power for each of the primary endpoints is 90% and power for both primary endpoints simultaneously is 80%. No multiplicity adjustment is needed for the primary endpoints since non-inferiority in both primary endpoints is required to declare non-inferior diagnostic accuracy (sensitivity/specificity) with synthetic MR images compared to conventional MR images. Secondary performance endpoints will be evaluated using a hierarchical testing procedure only if the pass criteria for the primary endpoints is fulfilled.

	Clinical Investigation Code:	Date
SyntheticMR	CIP-003, Version K	2023-12-21

#### 12.5 Pass / Fail Criteria

The study will be passed if non-inferiority of synthetic compared to conventional MR images can be established with respect to both primary performance endpoints *Sensitivity of pathological findings* and *Specificity of pathological findings* on the full analysis set using one-sided test, non-inferiority margin -0.05 and significance level  $\alpha = 0.025$ .

#### 12.6 Interim Analysis

No interim analysis will be performed.

# 12.7 Reporting of Deviations from the Original Statistical Analysis Plan (SAP)

Any deviations discovered throughout the study from the original Statistical Analysis Plan (SAP) described in this CIP, will be described with justification in a CIP amendment to the final report, as deemed appropriate.

# 12.8 Subgroups for Analysis

Separate analyses for adult and pediatric sup-populations will be performed. Separate analyses across readers will also be performed.

#### 12.9 Procedures that Take into Account all the Data

Outliers will be included in summary tables and listings, and will not be handled separately.

# 12.10 Missing, Unused or Spurious Data

Available data from prematurely withdrawn subjects will be included in the analysis as far as possible. Only pairs of synthetic and conventional images evaluated by the same reader will be included in the analysis.

# 12.11 Exclusion of Particular Information from the Testing of the Hypothesis

If only one type of image (either synthetic or conventional) of an image pair is evaluated by a reader, this image read will be excluded from the analysis.

	Clinical Investigation Code:	Date
SyntheticMR	CIP-003, Version K	2023-12-21

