#### 6.3 Device Traceability

Device traceability is maintained in the clinical investigation by creating a new version of SyMRI that is used specifically in the clinical investigation. All contrast weighted images that will be used in the investigation are generated by SyntheticMR with this version after all subjects has been recruited and before the image reading can start. When the contrast weighted images are exported from SyMRI to DICOM format, the SyMRI software store relevant version information in DICOM tag SyntheticMR private group (3005), thus ensuring full traceability on the contrast weighted images back to the

	Clinical Investigation Code:	Date
SyntheticMR	CIP-003, Version K	2023-12-21

investigational device. The SyMRI software is not sent to the readers or sites for the purpose of the investigation.

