#### 9.5 Claims and Intended Performance of the Investigational Device

When interpreted by a trained physician, the information from SyMRI can provide information useful in determining diagnosis.

T1w and T2w images from SyMRI can replace conventional T1w and T2w images of similar resolution and provide the same determination of radiological findings.

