SyntheticMR	CIP-003, Version K	2023-12-21

A subject is defined as evaluable in the study if they have completed the necessary scans as described in this protocol. If a sequence is missing, or if settings did not follow the acquisition parameters (e.g resolution), or if the subject did not complete all scans, the subject images will be excluded from the image review.

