#### 10.4.6 Subject Withdrawal, Discontinuation, or Lost to Follow-up

Subjects are free to discontinue participation in the clinical investigation at any time and are not required to give a reason for their decision. However, subjects who discontinue the investigation should always be asked about the reason(s) for their discontinuation and about the presence of any adverse event (AE) /adverse device effect (ADE) and, if possible, be assessed by an investigator. Discontinuation from the clinical investigation will not affect the future treatment/care of the subject.

If the subject will withdraw his/her consent no further data will thereafter be recorded. Data collected up to the date of withdraw of informed consent will be used in the data analysis and for the Clinical Investigation Report (CIR). In case of withdrawal, all AEs/ADEs should be followed up.

Subjects may be withdrawn from the clinical investigation and assessments at any time, if deemed necessary by the Principal Investigator.

Specific reasons for withdrawal of subjects from this clinical investigation are:

- a) The decision of a subject to withdraw from the investigation (including if the subject withdraws informed consent);
- b) The Principal Investigator deems the subject unfit for the investigation or suspects poor CIP compliance;
- c) The subject is not able to lay still in the MRI, causing poor quality of the MRI scans;
- d) The Principal Investigator deems it is in the subject's best interest to be taken out of this investigation, e.g. due to claustrophobia.

Incorrectly enrolled subjects will be withdrawn from further assessments.

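### Does dropping unpaired reads hide synthetic images that could not be generated?

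*Combined protocol and SAP*

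**What the plan says.** Section 12.11 removes a read that has no partner: "If only one type of image (either synthetic or conventional) of an image pair is evaluated by a reader, this image read will be excluded". Section 12.10 says the same from the other side: "Only pairs of synthetic and conventional images evaluated by the same reader will be included in the analysis". Section 12.1.1 then defines the primary population by pairs: "The full analysis set consists of all subjects with at least one pair of synthetic-conventional MR image readings from at least one reader".

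Section 10.4.4 acts earlier. It defines an evaluable subject by completed scans and removes subjects with a missing or off-parameter sequence before review; likewise, "if the subject did not complete all scans, the subject images will be excluded from the image review". Section 10.4.6(c) lists as a withdrawal reason: "The subject is not able to lay still in the MRI, causing poor quality of the MRI scans". Section 12.10 adds: "Available data from prematurely withdrawn subjects will be included in the analysis as far as possible".

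On timing, section 6.3 says that the contrast-weighted images "are generated by SyntheticMR with this version after all subjects has been recruited and before the image reading can start". The claim in section 9.5 is that "T1w and T2w images from SyMRI can replace conventional T1w and T2w images of similar resolution". That sentence continues by tying the claim to reaching the same radiological findings.

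**The concern.** A subject can complete all four sequences, count as evaluable, and still have no synthetic image, for instance because DICOM tags that SyMRI needs were stripped during anonymization (section 10.7.2.1.2). That subject has no pair, is outside the full analysis set, and counts neither for nor against the device. By the time synthetic images are generated, recruitment is over and the subject's participation has ended, so the plan provides no rescan.

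The rule is symmetric, but exposure to loss may not be. Both synthetic contrasts depend on one acquisition plus a processing step, whereas the conventional T1w and T2w are separate acquisitions with no such step. If losses fell mainly on the synthetic side, complete-pair analysis would favour non-inferiority. The visible text plans no table that would show this. It is also not spelled out whether a subject with four compliant but poor scans may be left out of review.

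**Working it through.** **Inputs.** From sections 12.2 and 12.4: 90 pathological subjects and 90 controls, 5 readers, margin -0.05, one-sided alpha 0.025, power 90% per primary endpoint and 80% jointly. The list of planning assumptions is absent from the text available, so the following are assumed: a planned true difference of 0 (with -0.01 as a variant), conventional accuracy c of 0.80 to 1.00, and the number of losses.

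**The plan's own figure.** Sensitivity and specificity use separate subjects, so joint power is 0.90 × 0.90 = 0.81. The lower bound without independence is 1 - 0.10 - 0.10 = 0.80. The stated 80% is consistent with both.

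**Implied precision.** SE = 0.05/(1.960 + 1.2816) = 0.0154, so the SD of the per-subject difference is 0.0154 × √90 = 0.146. At an observed difference of 0 the lower limit is -1.96 × 0.0154 = -0.030.

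**Losses deleted, as planned.** With k subjects lost, lower limit = d - 1.96 × 0.1463/√(90 - k). For d = 0 this gives -0.030 at k = 1 and -0.031 at k = 2. Power at k = 2 is 89.4% instead of 90%.

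**Losses counted as failures.** Give each synthetic-side loss the value -c and each conventional-side loss +c. With ks and kc such losses, the mean is m = [(90 - ks - kc)d - c·ks + c·kc]/90, and the SE comes from the pooled sum of squares. Example with ks = 2, kc = 0, d = 0, c = 0.90:

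- m = -1.8/90 = -0.0200
- sum of squares = 88 × 0.1463² + 88 × 0.02² + 2 × 0.88² ≈ 3.47
- SE = √(3.47/90)/√90 = 0.0207
- lower limit = -0.0200 - 1.96 × 0.0207 = -0.061

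| Subjects lost (synthetic + conventional) | Lower limit, c = 0.80 to 1.00 |
|---|---|
| 1 + 0 | -0.044 to -0.048 |
| 2 + 0 | -0.056 to -0.065 |
| 1 + 1 | -0.039 to -0.043 |
| 2 + 2 | -0.046 to -0.053 |
| 0 + 2 | about -0.021 |

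If planning assumed a true difference of -0.01, SE = 0.04/3.2416 = 0.0123. Two synthetic losses then give -0.052 to -0.061, and one gives -0.039 to -0.044. A read lost by a single reader weighs one fifth as much; at c = 0.90 about nine such losses in separate subjects are needed to reach -0.050.

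**Sensitivity to the scoring.** The table assumes that a subject without synthetic images would be read wrongly by all five readers. If half the accuracy were retained (c = 0.90, so each loss is worth -0.45), two losses give m = -0.9/90 = -0.0100, SE = 0.0168 and a lower limit of -0.043. Non-inferiority then stands.

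**Can the losses arise?**

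- *Poor images* are not lost. All readers read all images (10.7.3.2), the finding classes offer no non-diagnostic option (10.7.5.1), and even an image rated at the bottom of the quality scale (10.7.5.2) receives a class and is counted.
- *A processing crash* need not be permanent. The sponsor runs an automated script offline (13.2), and nothing bars a rerun.
- *Stripped tags* are guarded against by a test scan that is anonymized and checked, with the process adjusted if tags are lost (10.7.2.1.2). Nothing bars a fresh export from the site.
- *Failures at generation* are not invisible. Table 5 marks device deficiencies at that very step, the definition in 19.1 covers malfunction and inadequate performance, and incidence is a safety endpoint (10.2.4) summarized under 12.1.6.
- *Expected number*: section 12.3 anticipates no drop-out among evaluable subjects.

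**The case for a change.** The strongest argument for a change is that a claim of replacement should show how often the replacement was unavailable. Two losses in 90 is a small number, section 8.2 itself lists software crashes and data transfer errors as residual risks, and a non-gating sensitivity analysis with an exclusion table would cost almost nothing before reads begin. It is true that the planned analysis would show no shift in such a case, and that no visible text links device deficiencies to excluded pairs.

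Less survives of the proposed sensitivity analysis. The objective and hypotheses concern the accuracy of findings when both image sets are read, which is what complete pairs estimate; non-generation is a question of technical success. Scoring an absent image as wrong ignores the conventional FLAIR kept in the synthetic set (10.7.3.2), the intended use alongside at least one conventional acquisition (6.4), and the fallback to conventional MR in section 8.2. For a control it turns no image into five false positives. Nor does it read cleanly: equal 2 + 2 losses, which carry no bias, can reach -0.053. In simulation at a true all-subject difference of -0.05, its one-sided error is 0.036 at 1% loss and 0.045 at 2%, against the nominal 0.025.

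On image quality, the sections can be read together: 10.4.4 decides who enters review, 10.4.6(c) permits the investigator to withdraw a subject, and 12.10 keeps whatever data exist. Sites do not have access to the synthetic images, so such a withdrawal cannot be selected on how they look, although motion during the 3D-QALAS scan could still prompt one.

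**Conclusion.** The observation is correct but narrow. A subject whose synthetic T1w and T2w cannot be generated, even after a rerun or a new export, leaves the co-primary comparison and would appear only as a device deficiency. Bias towards non-inferiority needs net losses on the synthetic side. With an observed difference of 0, about two whole subjects of 90 would be needed, and only if every read is scored as wrong; one would not be enough. With an observed difference of -0.01 one would be (-0.056 at c = 0.90). All these figures rest on assumed losses, an assumed planned difference and assumed accuracy; the documents report no loss and expect none.

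No change to the plan follows. The pair rule is pre-specified, symmetric and suited to the stated hypotheses, and an added non-gating analysis would leave the primary test and pass criterion as they are. Listing excluded subjects and reads by image type and cause, with reference to the device deficiency records, is reporting detail that analysts would sensibly supply. Should losses occur, scoring them as incorrect for both image types could be shown as an extreme bound and labelled as such.
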